6.2 IMPORTANT PROTOCOL DEVIATIONS

Data discrepancies and deviations from the CTP will be identified for all treated subjects.

Section 7.3 of the CTP: *Important protocol deviation (IPD) categories will be suggested in the Integrated Quality and Risk Management Plan (IQRMP), IPDs will be identified no later than in the Report Planning Meeting, and the IPD categories will be updated as needed.*

Consistency check listings (for identification of deviations of time windows) and a list of protocol deviations (e.g. deviations in drug administration, in blood sampling times, etc.) will be provided to be discussed at the combined report planning and database lock meeting (RPM/DBLM). At this meeting, all manual deviations identified at the sites by the CRAs and deviations too complex to program will be reviewed by the trial team to decide which are considered important. For definition of important protocol deviations (iPD), and for the process of identification of these, refer to the Boehringer Ingelheim (BI) SOP "Identify and Manage Important Protocol Deviations (iPD)" (2).

If any iPDs are identified, they are to be summarised into categories and will be captured in the RPM minutes via an accompanying Excel spreadsheet (3).

The iPDs will be summarised and listed.

6.3 SUBJECT SETS ANALYSED

Section 7.3 of the CTP:

- *Treated set (TS): The treated set includes all subjects who were treated with at least one dose of study drug. The treated set will be used for safety analyses.*
- *Pharmacokinetic parameter analysis set (PKS): This set includes all subjects in the treated set (TS) who provide at least one PK endpoint that was defined as primary and was not excluded due to a protocol deviation relevant to the evaluation of PK or due to PK non-evaluability (as specified in the following subsection 'Pharmacokinetics'). Thus, a subject will be included in the PKS, even if he contributes only one PK parameter value for one period to the statistical assessment. Descriptive and model based analyses of PK parameters will be based on the PKS.*

[...]

Plasma concentration data and parameters of a subject will be included in the statistical pharmacokinetic (PK) analyses if they are not flagged for exclusion due to a protocol deviation relevant to the evaluation of PK (to be decided no later than in the Report Planning Meeting) or due to PK non-evaluability (as revealed during data analysis, based on the criteria specified below). Exclusion of a subject's data will be documented in the CTR.

Relevant protocol deviations may be

- *Incorrect trial medication taken, i.e. the subject received at least one dose of trial medication the subject was not assigned to*
- *Incorrect dose of trial medication taken*
- *Use of restricted medications*

Plasma concentrations and/or parameters of a subject will be considered as non-evaluable, if for example

- *The subject experienced emesis at or before two times median t_{max} . Median t_{max} is to be taken either from the median t_{max} for the reference treatment or from median t_{max} for the test treatment, depending on whether the subject had experienced emesis after taken the test or the reference treatment. Median t_{max} is to be determined excluding the subjects experiencing emesis.*
- *A predose concentration of BI 894416 is $>5\% C_{max}$ value of that subject in the respective treatment period*
- *Missing samples/concentration data at important phases of PK disposition curve*

The descriptive analysis of PK concentrations will be based on the ADS ADPC as described at the beginning of [Section 7](#).

Table 6.3: 1 Subject sets analysed

Class of endpoint	Subject set	
	TS	PKS
Analyses of PK endpoints		X
Safety parameters	X	
Demographic/baseline parameters	X	
Important protocol deviations	X	
Disposition	X	

6.5 POOLING OF CENTRES

This section is not applicable, because the study was performed in only one centre.

6.6 HANDLING OF MISSING DATA AND OUTLIERS

Handling of missing data and outliers will be performed as described in the CTP, Section 7.5.

The only exceptions where imputation might be necessary for safety evaluation are AE dates. Missing or incomplete AE dates are imputed according to BI standards (see 001-MCG-156_RD-01 ([4](#))).

Missing data and outliers of PK data are handled according to BI standards (see 001-MCS-36-472_RD-01) ([5](#)).

6.7 BASELINE, TIME WINDOWS AND CALCULATED VISITS

For vital signs, the baseline is defined as the last measurement before administration of BI 894416 in each period.

For laboratory, the baseline is defined as the measurement prior to first drug administration (in Visit 2).

Section 6.1 of the CTP: *Exact times of measurements outside the permitted time windows will be documented. The acceptable time windows for screening and the end of trial examination are provided in the Flow Chart.*

Study measurements and assessments scheduled to occur 'before' trial medication administration on Day 1 are to be performed and completed within a 3 h-period prior to the trial drug administration. The acceptable deviation from the scheduled time for vital signs, ECG, and laboratory tests will be ± 1 h.

[...]

Starting from 48 hours after BI 894416 administration a time window of ± 120 min will be allowed for all study activities.

Adherence to time windows will be checked via the consistency check listings at the RPM/DBLM.

Unscheduled measurements of laboratory data and vital signs data will be assumed to be repeat measurements of the most recent scheduled measurement (e.g. for follow-up or confirmation of a particular value). Therefore, unscheduled measurements will be assigned to the planned time point of the previous scheduled measurement.

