1. Subject must be informed and written informed consent obtained prior to starting any screening procedures. Screening procedures include physical examination, neurological examination, check of vital signs, ECG, safety laboratory (including drug screening), demographics (including determination of body height and weight, smoking status and alcohol history), relevant medical history, concomitant therapy and review of inclusion/exclusion criteria. Pharmacogenetic samples will be collected if needed.
2. The time is approximate; the procedure is to be performed and completed within the 3 h prior to drug administration.
3. If several actions are indicated at the same time, the intake of meals will be the last action.
4. At the end of trial (EoTrial) visit, the EoTrial examination includes physical examination, neurological examination, vital signs, ECG, safety laboratory, recording of AEs and concomitant therapies.
5. Only urine drug screening and alcohol breath test will be done at this time
6. AEs and concomitant therapies will be recorded throughout the trial, but will be specifically asked for at the times indicated in the Flow Chart above.
7. Unscheduled neurological examinations may be added at any time during the trial for individual volunteers or the whole treatment group, e.g., in case of neurological adverse events, if assessed as necessary by the investigator.
8. Letters A, B, and C define different sets of safety laboratory examinations (see Section [5.2.3](#))
9. Safety laboratory to be taken and to be medically evaluated within 5 days (within ~122 hours) prior to administration of study drug; this ambulatory visit including safety laboratory and adverse event questioning can be omitted if the screening examination is performed on Days -5, -4, -3, -2, or -1. Only prior to visit 2.

TABLE OF CONTENTS

TITLE PAGE	1
CLINICAL TRIAL PROTOCOL SYNOPSIS	2
FLOW CHART	4
TABLE OF CONTENTS	5
ABBREVIATIONS	9
1. INTRODUCTION.....	12
1.1 MEDICAL BACKGROUND.....	12
1.2 DRUG PROFILE	12
1.2.1 Residual Effect Period	13
1.3 RATIONALE FOR PERFORMING THE TRIAL	13
1.4 BENEFIT - RISK ASSESSMENT	13
1.4.1 Expected benefit to the target population.....	13
1.4.2 Procedure-related risks	14
1.4.3 Drug-related risks and safety measures.....	14
1.4.4 Overall assessment of benefit-risk ratio.....	17
2. TRIAL OBJECTIVES AND ENDPOINTS.....	19
2.1 MAIN OBJECTIVES, PRIMARY AND SECONDARY ENDPOINTS	19
2.1.1 Main objectives.....	19
2.1.2 Primary endpoints	19

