4.1.3 Method of assigning subjects to treatment groups

The randomisation list will be provided to the trial site in advance.

Subjects will be allocated to treatment sequences prior to the first administration of trial medication in the morning of Day 1 (Visit 2). For this purpose, numbers of the randomisation

Proprietary confidential information © 2019 Boehringer Ingelheim International GmbH or one or more of its affiliated companies

list will be allocated to the subjects by drawing lots. Subjects are then assigned to a treatment sequence according to the randomisation list.

Once a subject number has been assigned, it cannot be reassigned to any other subject.

The randomisation procedure is described in Section [7.6](#).

All subjects may be treated in one cohort, i.e. all subjects may receive treatment on the same calendar day. In case this is not feasible (e.g., due to logistical or recruitment reasons), the group may be split into several cohorts as required. Treatment of all subjects on the same calendar day is acceptable from a safety point of view (for safety margin to exposure in previous SRD trial 1371-0001 refer to Section [4.1.2](#); for discussion of study-associated risks and safety measures see Section [1.4](#)).

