5.2.3 Safety laboratory parameters

For the assessment of laboratory parameters, blood and urine samples will be collected by the trial site at the times indicated in the Flow Chart after the subjects have fasted for at least 10 h. For retests, at the discretion of the investigator or designee, overnight fasting is not required.

The parameters that will be determined are listed in Tables [5.2.3: 1](#) and [5.2.3: 2](#). Reference ranges will be provided in the ISF, Section 10.

Manual differential white blood cell count or urine sediment examinations will only be performed if there is an abnormality in the automatic blood cell count or in the urinalysis, respectively.

Proprietary confidential information © 2019 Boehringer Ingelheim International GmbH or one or more of its affiliated companies

Table 5.2.3: 1

Routine laboratory tests

Functional lab group	BI test name [comment/abbreviation]	A ¹	B ¹	C ¹
Haematology	Haematocrit Haemoglobin Red Blood Cell Count/Erythrocytes White Blood Cells/Leucocytes Platelet Count/Thrombocytes (quant)	X X X X X	X X X X X	X X X X X
Automatic WBC differential, relative	Neutrophils/Leukocytes; Eosinophils/Leukocytes; Basophils/ Leukocytes; Monocytes/Leukocytes; Lymphocytes/Leukocytes	X	X	X
Automatic WBC differential, absolute	Neutrophil, absol.; Eosinophils, absol.; Basophils, absol.; Monocytes, absol.; Lymphocytes, absol.	X	X	X
Manual differential WBC (if automatic differential WBC is abnormal)	Neut. Poly (segs); Neut. Poly (segs), absol.; Neutrophils Bands; Neutrophils Bands, absol.; Eosinophils/Leukocytes; Eosinophils, absol.; Basophils/ Leukocytes; Basophils, absol.; Monocytes/ Leukocytes; Monocytes, absol.; Lymphocytes/Leukocytes; Lymphocytes, absol.			
Coagulation	Activated Partial Thromboplastin Time Prothrombin time Prothrombin time – INR (International Normalization Ratio)	X X X	X X X	-- -- --
Enzymes	AST [Aspartate transaminase] /GOT, SGOT ALT [Alanine transaminase] /GPT, SGPT Alkaline Phosphatase Gamma-Glutamyl Transferase	X X X X	X X X X	X X -- --
Hormones	Thyroid Stimulating Hormone	X	--	--
Substrates	Glucose (Plasma) Creatinine Bilirubin, Total Bilirubin, Direct Protein, Total C-Reactive Protein (Quant)	X X X X X	X X X X X	-- X X -- X
Electrolytes	Sodium Potassium	X X	X X	X X

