Adverse events will be coded using the Medical Dictionary for Regulatory Activities (MedDRA). Frequency, severity, and causal relationship of AEs will be tabulated by treatment, system organ class, and preferred term. SAEs, AESIs (see Section [5.2.6.1](#)), and other significant AEs (according to ICH E3) will be listed separately.

Previous and concomitant therapies will be presented per treatment group without consideration of time intervals and treatment periods.

Laboratory data will be compared to their reference ranges. Values outside the reference range as well as values defined as possibly clinically significant will be highlighted in the listings. Additionally, differences from baseline will be evaluated.

Vital signs or other safety-relevant data will be assessed with regard to possible on-treatment changes from baseline.

Relevant ECG findings will be reported as AEs.

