4. CHANGES IN THE PLANNED ANALYSIS OF THE STUDY

All analyses as planned in the CTP will be performed and are described in more detail in this TSAP.

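### Does the laboratory baseline rule in SAP 6.7 leave the differences from baseline undefined?

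*SAP*

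**What the plan says.** SAP 6.7 gives two baseline rules, one after the other. The first reads "For vital signs, the baseline is defined as the last measurement before administration of BI 894416 in each period". The second reads "For laboratory, the baseline is defined as the measurement prior to first drug administration (in Visit 2"). The first rule picks the last value; the second carries no such word.

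The protocol's Flow Chart has two routine safety panels before the first dose. Set A is taken at screening (Visit 1, Day -21 to -1). Set C, a reduced panel, is taken at an ambulatory visit on Day -5 to -1, before the first period only. Footnote 9 says that "this ambulatory visit including safety laboratory and adverse event questioning can be omitted if the screening examination is performed on Days" -5 to -1. For the pre-dose time on Day 1, footnote 5 says "Only urine drug screening and alcohol breath test will be done at this time". Set B follows 24 h after each dose and at the end-of-trial visit.

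The baseline has a use. Protocol 7.3.4 says of laboratory data: "Additionally, differences from baseline will be evaluated". SAP 4 adds: "All analyses as planned in the CTP will be performed and are described in more detail in this TSAP". SAP 7.8.2 describes reference-range comparisons and descriptive statistics by planned time point, refers to a corporate laboratory standard, and states no baseline rule of its own.

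**The concern.** The SAP sentence is written as if there were one pre-dose panel, and there are two. Its closing bracket can also be attached in two ways.

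- If it describes the measurement, only set C can qualify, because no safety panel is drawn on Day 1 before dosing. Set C omits coagulation, alkaline phosphatase, GGT, glucose and urinalysis, all of which are measured after dosing in set B. Those tests would have no baseline, and a subject whose set C visit was omitted would have none at all.
- If it only says when the first dose is given, tests in both set A and set C have two qualifying values, and the sentence does not choose between them.

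Either way, two programmers might derive different differences from baseline from the same data. White cell count and the differential are among the tests in both panels, and protocol 1.4.3 names them for monitoring the immune-cell risk.

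**Working it through.** **Counts.** The documents state no figure to reproduce, so the check is a count of the tests named in protocol Table 5.2.3: 1. The conditional manual differential and urine sediment are left out, and TSH is not in set B.

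| Group | Set B | Set C |
|---|---|---|
| Haematology | 5 | 5 |
| Differential, relative | 5 | 5 |
| Differential, absolute | 5 | 5 |
| Coagulation | 3 | 0 |
| Enzymes | 4 | 2 |
| Substrates | 6 | 3 or 4 |
| Electrolytes | 2 | 2 |
| Urinalysis | 9 | 0 |
| Total | 39 | 22 or 23 |

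Set A contains all 39 set B tests. The substrates row names six tests but shows five marks per set, hence 3 or 4 in set C. The urinalysis row names nine and shows eight. Lost marks of this kind come from text extraction and are not errors in the plan.

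- In set B but not in set C: 39 - 23 = 16 to 39 - 22 = 17.
- Blood tests among these: 3 coagulation + 2 enzymes + 2 or 3 substrates = 7 or 8, out of 39 - 9 = 30. The other 9 are dipstick items, 8 of them labelled qualitative.
- In both pre-dose panels: 22 or 23.
- If the lost marks were true blanks, set B would have 37 to 38 tests, and 14 to 16 of them would be absent from set C.

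**Timing.** The set C visit is required when screening falls on Day -21 to -6. The two values are then at least 1 day apart (Day -6 to Day -5) and at most 20 days apart (Day -21 to Day -1). The oldest possible set A value is 21 days old at dosing (Day -21 to Day 1, with no Day 0). The Flow Chart's 122 h from 06:00 on Day -5 to 08:00 on Day 1 confirms that there is no Day 0: 5 × 24 + 2 = 122.

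**Which reading fits.** The bracket directly follows the words about the first administration. Protocol 4.1.3 places treatment allocation, ahead of that administration, "in the morning of Day 1 (Visit 2"), so the same label is attached to the dosing day. Footnote 9 confines the set C visit to the time before Visit 2. Taken literally, set C is then not a Visit 2 measurement, and the rule would give no baseline for any of the 39 tests in any subject. A rule that yields nothing is unlikely to be what was meant.

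**Result on that reading.**

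| Case | Pre-dose panels | Open choice |
|---|---|---|
| 16 to 17 tests not in set C | Set A only | None |
| All 39 tests, set C visit omitted | Set A only | None |
| 22 to 23 tests, both panels done | Set A and set C | Which value |

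Taking the last value before the first dose settles the third row and leaves every set B test with one baseline.

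**The case for a change.** The case for changing the text is fair. The reading that leaves tests without a baseline is not impossible: the Flow Chart prints the set C row under Visits 2 and 3, and protocol 6.2.2 counts Day -5 onwards as part of period 1. The vital-signs rule names the last value one sentence earlier, so its absence for laboratory could be taken as deliberate. The SAP is the document meant to settle derivations before programming, this one feeds a planned analysis, and one sentence would close the gap at no cost in data.

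What stands is that the wording is loose and that the laboratory rule omits the selector. The rest is weaker. The gap arises only for tests in both panels, in subjects who had both. A definite singular for the measurement before dosing most naturally means the one closest to it, and the neighbouring rule points the same way. The claim that two programmers would differ also supposes that the corporate laboratory standard cited in SAP 7.8.2 has no default. That standard is not available here, so the point cannot be settled in either direction.

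**Conclusion.** No change to the plan follows. This is missing detail that an analyst would fill in the ordinary way, by taking the last pre-dose value of each test, from set C where measured and otherwise from set A. Followed in that way, the plan gives sound descriptive laboratory output.

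The open choice covers 22 to 23 of 39 tests, in subjects with both panels. The documents do not say how many of the 14 planned subjects that will be. The figure of 16 to 17 tests without a baseline belongs to the less natural reading and should not be taken as the size of the problem. Where the baseline is an older screening value, that follows from the sampling schedule and would be the same under any wording of the rule.

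Nothing beyond the descriptive differences from baseline depends on this. The pharmacokinetic endpoints do not use it, reference-range flags compare each value with its range, and the hepatic-injury definition is set against the upper limit of normal.

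The conclusion assumes that the bracket locates the first dose and that every test named in the table is in set B. If the lost marks were true blanks, the counts would move by one or two tests and the conclusion would not.

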6.2.2 Treatment periods

Each subject is expected to participate in 2 treatment periods (Days -5 to 3 in period 1 and Days 1, 2, and 3 in period 2). At least 5 days will separate drug administrations in the first and second treatment periods.

Proprietary confidential information © 2019 Boehringer Ingelheim International GmbH or one or more of its affiliated companies

On Day 1 of each treatment period, study participants will be admitted to the trial site and kept under close medical surveillance for at least 24 h following drug administration. The subjects will then be allowed to leave the trial site after formal assessment and confirmation of their fitness. On all other study days, subjects will be treated in an ambulatory fashion.

For details on time points and procedures for collection of plasma samples for PK analysis, refer to [Flow Chart](#) and Section [5.3.2](#).

The safety measurements performed during the treatment period are specified in Section [5.2](#) of this protocol and in the Flow Chart. For details on times of all other trial procedures, refer to the Flow Chart. AEs and concomitant therapy will be assessed continuously from screening until the end of trial examination.

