7.3.4 Safety analyses

Safety will be analysed based on the assessments described in Section [2.2.2.2](#). All treated subjects (TS, refer to Section [7.2](#)) will be included in the safety analysis. Safety analyses will be descriptive in nature and based on BI standards. No hypothesis testing is planned.

For all analyses, the treatment actually administered (= treatment at onset) to the subject will be used (any deviations from the randomised treatment will be discussed in the minutes of the Report Planning Meeting).

Treatments under fed and under fasted condition will be compared in a descriptive way. Tabulations of frequencies/proportions will be used to evaluate categorical (qualitative) data, and tabulations of descriptive statistics will be used to analyse continuous (quantitative) data.

Measurements (such as ECG, vital signs, or laboratory parameters) or AEs will be assigned to treatments (see Section [4.1](#)) based on the actual treatment at the planned time of the measurement or on the recorded time of AE onset (concept of treatment emergent AEs).

Therefore, measurements planned or AEs recorded prior to first intake of trial medication will be assigned to the screening period and those between trial medication intake and the trial medication intake in the next treatment period or the EoTrial Visit (whatever comes next) will be assigned to the respective treatment. In case of two or more treatments, the follow-up will be summarized according to the previous treatment. These assignments including the

Proprietary confidential information © 2019 Boehringer Ingelheim International GmbH or one or more of its affiliated companies

corresponding time intervals will be defined in detail in the TSAP. Note that AEs occurring after the last per protocol contact but entered before final database lock will be reported to Pharmacovigilance only and will not be captured in the trial database.

Additionally, further treatment intervals (analysing treatments) may be defined in the TSAP in order to provide summary statistics for time intervals, such as combined treatments, on-treatment totals, or periods without treatment effects (such as screening and follow-up intervals).

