7.8.2 Laboratory data

The analyses of laboratory data will be descriptive in nature and will be based on BI standards [001-MCG-157] ([10](#)).

Laboratory data will be analysed qualitatively via comparison of laboratory data to their reference ranges. Values outside the reference range as well as values defined as possibly clinically significant will be flagged in the data listings.

It is the investigator's responsibility to decide whether a lab value is clinically significantly abnormal or not (at the RPM/DBLM at the latest).

Descriptive statistics of laboratory data will be calculated by planned time point based on the worst value of the subject at that planned time point (or assigned to that planned time point).

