7.8.3 Vital signs

Descriptive statistics over time including change from baseline will be performed for vital signs (blood pressure and pulse rate). In the listing the difference from baseline will also be displayed.

For vital signs, descriptive statistics will be calculated by planned time point based on the last value of the subject at that planned time point (or assigned to that planned time point).

Clinically relevant findings in vital signs will be reported as AEs.

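### SAP 6.7 carries unscheduled values back with no stop at a dose, so a lab taken after dose 2 and before its 24 h sample is placed, read literally, at the period 1 24 h time point

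*SAP*

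**What the plan says.** SAP 6.7 treats unscheduled laboratory and vital-sign values as repeats of the latest scheduled one: "Therefore, unscheduled measurements will be assigned to the planned time point of the previous scheduled measurement". It names no limit by dose, period or elapsed time.

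Two rules then decide which value enters the by-time tables. For laboratory data, SAP 7.8.2 computes the statistics "based on the worst value of the subject at that planned time point (or assigned to that planned time point"). For vital signs, SAP 7.8.3 says "descriptive statistics will be calculated by planned time point based on the last value of the subject at that planned time point", and likewise includes values assigned to that time point.

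Protocol 7.3.4 assigns measurements and adverse events to treatments "based on the actual treatment at the planned time of the measurement or on the recorded time of AE onset". It adds that "measurements planned or AEs recorded prior to first intake of trial medication will be assigned to the screening period". The same sentence then assigns what falls between one intake and the next intake, or the end-of-trial visit, to the respective treatment. The detailed intervals are left to the SAP. SAP 6.1 defines phases that end at the next dose, but for adverse events only.

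The laboratory schedule comes from the Flow Chart and its footnotes. The Day 1 pre-dose entry is limited: "Only urine drug screening and alcohol breath test will be done at this time" (footnote 5). The ambulatory visit with laboratory set C "can be omitted if the screening examination is performed on Days -5, -4, -3, -2, or -1. Only prior to visit 2" (footnote 9). Protocol 6.2.2 gives the periods as "Days -5 to 3 in period 1 and Days 1, 2, and 3 in period 2".

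**The concern.** Treating an unscheduled value as a repeat is sensible when an abnormal result is being followed up. It stops being sensible once another dose has been given, because the value is then a new post-dose observation and does not confirm the earlier sample. Here the schedule leaves a stretch after each dose in which the previous scheduled laboratory sample predates that dose. After dose 2 that earlier sample belongs to the other period, and so to the other food condition.

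At stake is the descriptive comparison of fed and fasted safety data foreseen in protocol 7.3.4. An unscheduled lab taken because something looked abnormal is the kind of value a worst-value rule tends to select. It would then appear in a row for a time point several days before it was drawn, and possibly under the treatment the subject was not on.

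**Working it through.** The plan gives no figure to reproduce. The check applies the SAP 6.7 rule to the Flow Chart schedule.

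**Inputs**
- Routine labs: screening (set A); set C before visit 2 only, which may be omitted; set B at 24 h in each period; set B at end of trial (Flow Chart, footnotes 5 and 9).
- The Day 1 pre-dose drug screen cannot serve as the previous scheduled value, because its results are not entered in the database. The breath-test results are not reported in the trial report (protocol 5.2.3).
- Vital signs: screening; pre-dose, 1 h, 2 h and 24 h in each period; end of trial (Flow Chart).
- Doses at least 5 days apart (protocol 6.2.2). I take the minimum, 5 × 24 = 120 h, and count hours from dose 1.
- Window of ±1 h for labs and vital signs (protocol 6.1).

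**Rule:** assigned time point = latest scheduled measurement at or before the unscheduled time. Lag = unscheduled time − assigned time.

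**Labs around dose 2.** The period 1 24 h sample is at 24 h; the period 2 24 h sample is at 120 + 24 = 144 h.

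| Unscheduled lab | Hours from dose 1 | Assigned to | Lag (h) | Dose in between? |
|---|---|---|---|---|
| 1 h before dose 2 | 119 | Period 1, 24 h | 119 − 24 = 95 | No |
| 0.5 h after dose 2 | 120.5 | Period 1, 24 h | 120.5 − 24 = 96.5 | Yes |
| 6 h after dose 2 | 126 | Period 1, 24 h | 126 − 24 = 102 | Yes |
| 23 h after dose 2 | 143 | Period 1, 24 h | 143 − 24 = 119 | Yes |
| 30 h after dose 2 | 150 | Period 2, 24 h | 150 − 144 = 6 | No |

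The rule works in the first and last rows and fails in the three between. A longer washout lengthens the lags of the first four rows and changes no assignment.

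**Labs around dose 1.** An unscheduled lab 0.5, 6 or 23 h after dose 1 goes to set C, or to screening if set C was omitted. This is a pre-dose time point, not the other treatment.

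**Vital signs.** A value 0.5 h after either dose goes to that period's own pre-dose point, where the last-value rule would use it in place of the scheduled reading. It does not change period, because each period has its own pre-dose reading.

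**Scope per subject**
- Labs: 5 scheduled times, so 4 intervals (3 without set C). Two contain a dose, and one of these, at dose 2, leads into the other period.
- Vital signs: 10 scheduled times, so 9 intervals. Two contain a dose, and none leads into the other period.
- Exposed time after each dose: labs 24 h (24 ± 1 = 23 to 25 h); vital signs 1 h (1 ± 1 = 0 to 2 h).
- Weight in a row: each subject contributes one value. If rows pool both periods, 1/14 = 7.1%. If they are split by period or sequence, 14/2 = 7 subjects and 1/7 = 14.3%. The SAP does not say which layout is used, and dropouts would raise either share.

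**From time point to treatment.** SAP 6.7 fixes a time point, not a treatment. One reading of protocol 7.3.4 links measurements to treatment by planned time. The only planned time an unscheduled value has is the one SAP 6.7 gives it, which here lies in period 1. The other reading uses the intake-to-intake clause: the value was taken after dose 2 and stays under the second treatment. Its row and its treatment would then disagree. Neither document chooses between the readings for laboratory values.

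**The case against.** A reader might infer that such a lab is certain to be counted under the wrong food condition. The documents do not support that. The intake-to-intake clause in protocol 7.3.4 is a dose boundary, and SAP 4 says that all analyses planned in the protocol will be performed, so the clause remains in force. It can fairly be read as keeping the value under the second treatment. Whether it covers actual or planned times is unclear, so it does not settle the matter, but it does make the wrong treatment one reading only.

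Second, SAP 6.1 refers the detailed handling of treatments to the ADS plan and the reviewers guide, and SAP 7.8.2 bases laboratory analyses on a sponsor guideline. A boundary may stand there. These documents are not available, and SAP 6.7 does not point to one.

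Third, the consequences are limited. Safety is descriptive with no hypothesis testing. Individual values are listed by visit and, where appropriate, actual treatment (SAP 7), and out-of-range laboratory values are flagged. Clinically relevant changes are recorded as adverse events, which follow their own onset time. Protocol 5.2.6.1.4 foresees an unscheduled blood test in one situation, but nothing suggests one within 24 h of a dose. All of this stands and keeps the point minor.

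What remains is that the literal rule gives the wrong row, and none of these arguments changes that.

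**Conclusion.** The point holds as a minor one. Under the literal text of SAP 6.7, an unscheduled lab after dose 2 and before its 24 h sample is placed at the period 1 24 h time point. It enters that row's statistics if it is the subject's worst value there. That it could also be summarised under the other food condition is a possible reading of protocol 7.3.4, not an established result.

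The dose 1 labs and the first-hour vital signs are secondary: they reach a pre-dose row but not the other treatment. A reader might also infer that the baselines are contaminated. They are not, because SAP 6.7 defines both as measurements before administration. Adverse event tables, listings and pharmacokinetic results are unaffected as well.

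The frequency is unknown and may be zero. The conclusion assumes that no boundary exists in the ADS plan or the laboratory guideline.

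**What to change.** In SAP 6.7, state that an unscheduled value is carried back only to a scheduled measurement taken after the most recent dose; values before the first dose keep the present rule. Where a dose lies in between, assign the value by actual time to the treatment last taken. Show it as an unscheduled post-dose value under that treatment, in the listings and, if tabulated, in a row of its own, and not in a row from before that dose. A separate row keeps a possibly abnormal early value visible in the tables. Follow-up repeats that do not cross a dose need no change and no time limit.

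If the ADS plan or laboratory guideline already contains this boundary, a reference to it in SAP 6.7 is enough.

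The cost is one or two sentences and one extra condition in the derivation. The date and time of each dose are already to be listed (SAP 7.7). The downside is that the few values that cross a dose leave the scheduled by-time rows.
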